#### 8.3.10.1. Definitions

Evaluable for toxicity: All patients will be evaluable for toxicity from the time of consent.

Evaluable for objective response: Only those patients who have measurable disease present at baseline, have received at least one cycle of therapy, and have had their disease re-evaluated will be considered evaluable for response. These patients will have their response classified according to the definitions stated below. (NOTE: Patients who exhibit objective disease progression prior to the end of Cycle 1 will also be considered evaluable.)

Evaluable Non-Target Disease Response: Patients who have lesions present at baseline that are evaluable but do not meet the definitions of measurable disease, have received at least one cycle of therapy, and have had their disease re-evaluated will be considered evaluable for non-target disease. The response assessment will be based on the presence, absence, or unequivocal progression of the lesions.

#### 8.3.10.2. Disease Parameters

Measurable disease: For the purposes of this study, measurable lesions are defined according to RECIST v1.1 criteria. All tumor measurements must be recorded in mm (or decimal fractions of centimeters).

NOTE: Tumor lesions that are situated in a previously irradiated area might or might not be considered measurable.

Malignant lymph nodes: To be considered pathologically enlarged and measurable, a lymph node must be  $\geq 15$  mm in short axis when assessed by computerized tomography (CT) scan (CT scan slice thickness recommended to be no greater than 5 mm). At baseline and in follow-up, only the short axis will be measured and followed.

Non-measurable disease: All other lesions (or sites of disease), including small lesions (longest diameter <10 mm or pathological lymph nodes with  $\geq$ 10 to <15 mm short axis), are considered non-measurable disease. Bone lesions, leptomeningeal disease, ascites, pleural/pericardial effusions, lymphangitis cutis/pulmonis, inflammatory breast disease, and abdominal masses (not followed by CT or magnetic resonance imaging [MRI]), are considered as non-measurable.

NOTE: Cystic lesions that meet the criteria for radiographically defined simple cysts should not be considered as malignant lesions (neither measurable nor non-measurable) since they are, by definition, simple cysts.

'Cystic lesions' thought to represent cystic metastases can be considered as measurable lesions, if they meet the definition of measurability described above. However, if non-cystic lesions are present in the same patient, these are preferred for selection as target lesions.

Target lesions: All measurable lesions up to a maximum of 2 lesions per organ and 5 lesions in total, representative of all involved organs, should be identified as target lesions and recorded and measured at baseline. Target lesions should be selected on the basis of their size (lesions

with the longest diameter), be representative of all involved organs, but in addition should be those that lend themselves to reproducible repeated measurements. It may be the case that, on occasion, the largest lesion does not lend itself to reproducible measurement; in such circumstance, the next largest lesion which can be measured reproducibly should be selected. A sum of the diameters (longest for non-nodal lesions, short axis for nodal lesions) for all target lesions will be calculated and reported as the baseline sum diameters. If lymph nodes are to be included in the sum, then only the short axis is added into the sum. The baseline sum diameters will be used as a reference to further characterize any objective tumor regression in the measurable dimension of the disease.

Non-target lesions: All other lesions (or sites of disease) including any measurable lesions over and above the 5 target lesions should be identified as non-target lesions and should also be recorded at baseline. Measurements of these lesions are not required, but the presence, absence, or rare cases of unequivocal progression of each should be noted throughout follow-up.

#### **8.3.10.3.** Methods for Evaluation of Measurable Disease

All measurements should be taken and recorded in metric notation using a ruler or calipers. All baseline evaluations should be performed as closely as possible to the beginning of treatment and never more than 4 weeks before the beginning of the treatment.

The same method of assessment and the same technique should be used to characterize each identified and reported lesion at baseline and during follow-up. Imaging-based evaluation is preferred to evaluation by clinical examination unless the lesion(s) being followed cannot be imaged and are only assessable by clinical examination. Methods allowable for disease evaluation are as follows:

- Clinical examination: For skin lesions, documentation by color photography, including a ruler to estimate the size of the lesion, is recommended. Clinical lesions will only be considered measurable when they are superficial (eg, skin nodules and palpable lymph nodes) and ≥10 mm diameter as assessed using calipers (eg, skin nodules).
- Chest x-ray: Lesions on chest x-ray are acceptable as measurable lesions when they are clearly defined and surrounded by aerated lung. However, CT is preferable.
- Conventional CT and MRI: A CT scan may be used to measure the lesion if the CT slice thickness is 5 mm or less. If CT scans have slice thickness greater than 5 mm, the minimum size for a measurable lesion should be twice the slice thickness. MRI is also acceptable in certain situations (eg, for body scans). For both scanning methods, technical specifications of the scanning sequences used should be optimized for the evaluation of the type and site of disease. The modality used at follow-up should be the same as was used at baseline, and the lesions should be measured/assessed on the same pulse sequence. Ideally, the same type of scanner should be used, and the image acquisition protocol should be followed as closely as possible to prior scans. Body scans should be performed with breath-hold scanning techniques, if possible.
- Positron emission tomography (PET)-CT: Combined PET-CT is not always of optimal diagnostic CT quality for use with RECIST measurements. However, if the site can document that the CT performed as part of a PET-CT is of identical

diagnostic quality to a diagnostic CT (with IV and oral contrast), then the CT portion of the PET-CT can be used for RECIST measurements and can be used interchangeably with conventional CT in accurately measuring cancer lesions over time.

Fluorodeoxyglucose (FDG)-PET: FDG-PET scanning is optional and may be used to complement CT scanning in assessment of progression (particularly possible 'new' disease). New lesions on the basis of FDG-PET imaging can be identified according to the following algorithm:

- 1. Negative FDG-PET at baseline, with a positive FDG-PET at follow-up is a sign of PD based on a new lesion.
- 2. No FDG-PET at baseline and a positive FDG-PET at follow-up: If the positive FDG-PET at follow-up corresponds to a new site of disease confirmed by CT, this is PD. If the positive FDG-PET at follow-up is not confirmed as a new site of disease on CT, additional follow-up CT scans are needed to determine if there is truly progression occurring at that site (if so, the date of PD will be the date of the initial abnormal FDG-PET scan). If the positive FDG-PET at follow-up corresponds to a pre-existing site of disease on CT that is not progressing on the basis of the anatomic images, this is not PD.
- 3. FDG-PET may be used to upgrade a response to a CR in a manner similar to a biopsy in cases where a residual radiographic abnormality is thought to represent fibrosis or scarring. The use of FDG-PET in this circumstance should be prospectively described in the protocol and supported by disease-specific medical literature for the indication. However, it must be acknowledged that both approaches may lead to false positive CR due to limitations of FDG-PET and biopsy resolution/sensitivity.

NOTE: A 'positive' FDG-PET scan lesion means one that is FDG avid with an uptake greater than twice that of the surrounding tissue on the attenuation corrected image.

Ultrasound is not useful in assessment of lesion size and should not be used as a method of measurement. If new lesions are identified by ultrasound in the course of the study, confirmation by CT or MRI is advised.

Cytology and histology techniques can be used to differentiate between PR and CR in rare cases (eg, residual lesions in tumor types, such as germ cell tumors, where known residual benign tumors can remain).

The cytological confirmation of the neoplastic origin of any effusion that appears or worsens during treatment when the measurable tumor has met criteria for response or SD is mandatory to differentiate between response or SD (an effusion may be a side effect of the treatment) and PD.

## 8.3.10.4. Response Criteria

#### Evaluation of Target Lesions

CR: Disappearance of all target lesions. Any pathological lymph nodes (whether target or non-target) must have reduction in short axis to <10 mm.

PR: At least a 30% decrease in the sum of the diameters of target lesions, taking as reference the baseline sum diameters.

PD: At least a 20% increase in the sum of the diameters of target lesions, taking as reference the smallest sum on study (this includes the baseline sum if that is the smallest on study). In addition to the relative increase of 20%, the sum must also demonstrate an absolute increase of at least 5 mm. (NOTE: the appearance of one or more new lesions is also considered progression).

SD: Neither sufficient shrinkage to qualify for PR nor sufficient increase to qualify for PD, taking as reference the smallest sum diameters while on study.

#### Evaluation of Non-Target Lesions

CR: Disappearance of all non-target lesions and normalization of tumor marker level. All lymph nodes must be non-pathological in size (<10 mm short axis).

NOTE: If tumor markers are initially above the upper normal limit, they must normalize for a patient to be considered in complete clinical response.

Non-CR/Non-PD: Persistence of one or more non-target lesion(s) and/or maintenance of tumor marker level above the normal limits.

PD: Appearance of one or more new lesions and/or unequivocal progression of existing non-target lesions. Unequivocal progression should not normally trump target lesion status. It must be representative of overall disease status change, not a single lesion increase.

Although a clear progression of "non-target" lesions only is exceptional, the opinion of the treating physician should prevail in such circumstances, and the progression status should be confirmed at a later time by the review panel (or PI).

#### 8.3.10.5. Evaluation of Best Overall Response

The best overall response is the best response recorded from the start of the treatment until disease progression/recurrence (taking as reference for PD the smallest measurements recorded since the treatment started). The patient's best response assignment will depend on the achievement of both measurement and confirmation criteria. Best overall response is described in Table 8 for patients with measurable disease and in Table 9 for patients with non-measurable disease.

## Table 8:Best Overall Response for Patients with Measurable Disease (ie, Target
Disease)

Target	Non-Target Lesions	New	Overall	Best Overall Response when
Lesions		Lesions	Response	Confirmation is Required
CR	CR	No	CR	≥4 weeks confirmation a
CR	Non-CR/Non-PD	No	PR	$\geq$ 4 weeks confirmation a
CR	Not evaluated	No	PR	
PR	Non-CR/Non-PD/not evaluated	No	PR	
SD	Non-CR/Non-PD/not evaluated	No	SD	Documented at least once $\geq 4$ weeks
				from baseline
PD	Any	Yes or	PD	no prior SD, PR, or CR
		No		
Any	$PD^{b}$	Yes or	PD	
		No		
Any	Any	Yes	PD	

Abbreviations: CR=complete remission; SD=stable disease; PD=progressive disease; PR=partial response; RECIST=Response Evaluation Criteria in Solid Tumors.

- a Only for non-randomized studies with response as primary endpoint.
- b In exceptional circumstances, unequivocal progression in non-target lesions may be accepted as disease progression.
- Note: Patients with a global deterioration of health status requiring discontinuation of treatment without objective evidence of disease progression at that time should be reported as "symptomatic deterioration." Every effort should be made to document the objective progression even after discontinuation of treatment.

See RECIST v1.1 manuscript for further details on what is evidence of a new lesion.

NOTE: For purposes of this trial, confirmation of response will occur at 6 weeks after the response-defining measurements rather than the 4-week point specified in the RECIST v1.1 criteria.

Table 9:	Best Overall Response for Patients with Non-Measurable Disease (ie,
	Non-Target Disease)

Non-Target Lesions	New Lesions	Overall Response
CR	No	CR
Non-CR/non-PD	No	Non-CR/non-PD a
Not all evaluated	No	not evaluated
Unequivocal PD	Yes or No	PD
Any	Yes	PD

Abbreviations: CR=complete remission; PD=progressive disease; SD=stable disease

a 'Non-CR/non-PD' is preferred over 'stable disease' for non-target disease since SD is increasingly used as an endpoint for assessment of efficacy in some trials so to assign this category when no lesions can be measured is not advised

#### 8.3.10.6. Duration of Response

Duration of overall response: The duration of overall response is measured from the time measurement criteria are met for CR or PR (whichever is first recorded) until the first date that recurrent or PD is objectively documented (taking as reference for PD the smallest measurements recorded since the treatment started).

The duration of overall CR is measured from the time measurement criteria are first met for CR until the first date that PD is objectively documented.

Duration of SD: The duration of SD is measured from the start of the treatment until the criteria for progression are met, taking as reference the smallest measurements recorded since the treatment started, including the baseline measurements.

#### 8.3.11. Laboratory Assessments

Blood and urine samples for laboratory assessments will be collected at the time points specified in Table 4. Specific complete blood count (CBC) with differential, complete serum chemistry, and urinalysis assessments are listed in Table 10. Samples will be collected in accordance with the site's usual procedures and analyzed by the site's local laboratory for CBC with differential, complete serum chemistry, and urinalysis.

CBC with Differential	Complete Serum Chemistry	Urinalysis	Other
Hematocrit	Sodium	Specific gravity	Serum β-hCG b
Hemoglobin	Potassium	Protein	PT (INR)
Platelet count	Phosphorus	pН	aPTT
Red blood cell count	Glucose	Glucose	TSH
Total and differential	Total protein	Ketones	Cortisol (morning)
white blood cell count	BUN	Blood	АСТН
ANC Absolute lymphocyte count	Serum creatinine CrCl Albumin Total bilirubin ALT AST LDH ALK-P CO 2 or bicarbonate a Uric acid Calcium Chloride Magnesium Direct bilirubin, if total bilirubin is elevated above the upper limit of normal	Microscopic examination of sediment, only if urinalysis dipstick results are abnormal (2+ or higher ) Urine pregnancy test b	

 Table 10:
 Clinical Laboratory Assessments

Abbreviations: ACTH=adrenocorticotropic hormone; ALK-P=alkaline phosphatase; ALT=alanine aminotransferase; ANC=absolute neutrophil count; aPTT=activated partial thromboplastin time; AST=aspartate aminotransferase; BUN=blood urea nitrogen; CBC=complete blood count; CO2=carbon dioxide; CrCl=creatinine clearance; hCG=human chorionic gonadotropin; INR=international normalized ratio; LDH=lactic dehydrogenase; PT=prothrombin time; TSH=thyroid-stimulating hormone.

a If considered standard of care in local region.

b Perform on women of childbearing potential only. If urine pregnancy test results cannot be confirmed as negative, a serum pregnancy test will be required.

Laboratory tests for screening should be performed within 10 days prior to the first dose of treatment. After Cycle 1, predose laboratory procedures can be conducted up to 72 hours prior to dosing on Day 1 of each cycle. Results must be reviewed by the Investigator or qualified designee and found to be acceptable prior to each dose of study drug.

If a site is unable to collect all specimens due to low hemoglobin or other issues such as vein access, specimens should be collected in the following order if required at the visit:

• Toxicity/safety specimens

•

### 8.3.11.1. Pregnancy Testing

A urine/serum pregnancy test will be administered to all women of childbearing potential at the time point(s) specified in Table 4. At the Screening Visit, results must be negative for the patient to be eligible for the study.

Section 12.5 provides guidance on the reporting requirements for pregnancies.

#### 8.3.11.2. Serology Testing

A blood sample for serology panel testing for hepatitis B surface antigen, anti-hepatitis C antibodies, and human immunodeficiency virus will be performed at screening only.

#### 8.3.12. Laboratory Correlative Studies

[figure not shown]
Specimens will be collected for several planned correlative studies (summarized in Table 16) at the time points specified in Table 4. Many samples will be processed and stored, to be run in batches. When blood volume is limited, correlative studies will be considered secondary to tests needed to make clinical decisions. Also, testing may be delayed or omitted if collecting the specimens may pose a danger to the patient, if samples cannot be processed or assayed, or if results are determined to be non-essential to achieving the objectives of the study.

#### 8.3.12.1. Correlative Studies With Biopsies

Collection of pretreatment tumor tissue (fresh biopsy via excisional, incisional, or core needle and large enough to show tissue architecture) is mandatory; if collecting pretreatment tissue is not possible (eg, inaccessible or patient safety concern), submission of archived specimen is possible upon agreement from the Sponsor. Obtaining a post-treatment (second) biopsy is mandatory in order to achieve protocol objectives and to study the TME post-treatment but may be bypassed for patient safety reasons only after discussions with the Sponsor. Biopsy-based correlatives are considered exploratory. Prioritization of biopsy specimens will be made based on technical considerations that will be included in the Laboratory Manual, total number of samples acquired, and feasibility of correlative study based on the above considerations.

The pretreatment biopsy will be collected after all screening assessments have been performed and before the first dose of pembrolizumab and ALKS 4230 on Cycle 1, Week 1, Day 1. The pretreatment specimen may be obtained up to 6 weeks (42 days) prior to initiation of treatment on Day 1, provided study informed consent has been obtained or the biopsy was performed as part of routine patient care. The post-treatment (second) biopsy will be performed on the same or similar tumor site during the first cycle of therapy at C1D12 or at any time from C1D8 through C1D19. Fine needle aspirates are not allowed for tissue sampling but may be used to localize active disease prior to tissue sampling.

The biopsies will be collected according to clinical site standard operating procedures (SOPs).

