## 7.1. Patient Inclusion Criteria

- 1. Is  $\geq 18$  years of age.
- 2. Is willing and able to provide informed consent.
- 3. Is willing and able to follow the study procedures as outlined in the protocol.
- 4. Must have a histologically or cytopathologically confirmed diagnosis of HNSCC region that is locally advanced or recurrent and no longer amenable to local surgical or radiation therapy and/or with evidence of metastatic disease. Both HPV-positive and -negative patients will be included.
- 5. Must have had prior PD-1:PD-L1 inhibition therapy with anti-PD-(L)1 therapy as the most recent systemic therapy with
  - a. (Group 1, Cohort 1) current SD (for  $\geq 12$  weeks by RECIST criteria v1.1) or
  - b. (Group 1, Cohort 2) current PR with no further reduction in tumor size or response for ≥8 weeks (ie, PR and not further improving)
  - c. (Group 2, Cohort 3) current PD with no prior response to anti-PD-(L)1 therapy after  $\geq 8$  weeks on anti-PD-(L)1 or
  - d. (Group 2, Cohort 4) current PD after prior achievement of a best response of SD or PR and after ≥8 weeks on anti-PD-(L)1 therapy

Some minimal intervening localized palliative radiotherapy or ablation therapy may be allowed upon review and agreement by the ION and Alkermes Medical Monitors.

- 6. Must have disease that is measurable by RECIST v1.1 criteria as determined by the treating physician and not confounded by prior treatment such as radiation. Patients with only 1 site of disease must be able to provide adequate tissue samples at the time of biopsy that will not affect the tumor size per RECIST v1.1 criteria.
- 7. Patients who have received standard or investigational anti-PD-(L)1 agents as the most recent systemic therapy must wait at least 3 weeks (with the exception of an anti-PD-[L]1 inhibitor that is dosed Q2W and in consultation with the ION and Alkermes Medical Monitors, in which case patients must wait at least 2 weeks) before enrollment into the study or 4 weeks if the half-life of the investigational agent is not known. Patients who have received standard or investigational agents other than anti-PD-(L)1 agents (including agents as part of a combination regimen with an anti-PD-[L]1 agent) must wait 8 weeks before enrollment into the study, unless discussed with and approved by the ION and Alkermes Medical Monitors on an individual basis.

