- 8. Patients must be willing to provide tumor tissue adequate for biomarker correlative studies at the time points specified in the protocol.

- 9. Patients should have readily accessible tumor for biopsy pre- and post-pembrolizumab and ALKS 4230 combination regimen. Biopsy should be excisional, incisional, or core needle and large enough to show tissue architecture.
- 10. Have a performance status of ≤2 on the Eastern Cooperative Oncology Group (ECOG) Performance Scale.
- 11. Demonstrate adequate organ function as defined in Table 3. All screening laboratories should be performed within 10 days of treatment initiation.

System	Laboratory Value
Hematological	
ANC	$\geq$ 1,000/µL without hematopoietic growth factor support
Platelet count	≥100,000/µL without transfusion support
Hemoglobin	$\geq 9 \text{ g/dL}$
Renal	
Serum creatinine OR	≤1.5×ULN OR
Measured or calculated a CrCl	
(glomerular filtration rate [GFR] can also	≥60 mL/min
be used in place of creatinine or CrCl)	
Hepatic	
	≤1.5×ULN OR
Serum total bilirubin	Direct bilirubin ≤ULN for patients with total bilirubin levels
	>1.5×ULN
AST and ALT	≤2.5×ULN OR
	$\leq$ 5×ULN for patients with liver metastases
Albumin	>2.5 mg/dL
Coagulation	
INR or PT aPTT	
 
≤1.5×ULN unless patient is receiving anticoagulant therapy.
 
If the patient is receiving anticoagulant therapy, the INR or PT needs to be within the therapeutic range of intended use of anticoagulants or deemed a safe level for the proposed biopsies by the biopsy surgeon or interventional radiologist.
 
≤1.5×ULN unless patient is receiving anticoagulant therapy. If the patient is receiving anticoagulant therapy, the aPTT needs to be within the therapeutic range of intended use of anticoagulants or deemed a safe level for the proposed biopsies by the biopsy surgeon or interventional radiologist.
 

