## 8. STUDY DESIGN

#### 8.1. Overall Study Design and Plan

The study will assess the antitumor efficacy of ALKS 4230 in combination with pembrolizumab in patients with advanced, recurrent, and/or HNSCC on treatment with an anti-PD-(L)1 antibody (pembrolizumab or nivolumab) without having achieved a CR.

The study is a multi-center, Phase 2, open-label therapy study in collaboration with ION. Patients must have received anti-PD-(L)1 therapy prior to enrollment into the study. After enrollment in the study, ALKS 4230 with pembrolizumab will be administered to 4 cohorts of patients with advanced, recurrent, and/or metastatic HNSCC who have received anti-PD-(L)1 therapy whose current response is as follows:

- Cohort 1: SD, defined as  $\geq 12$  weeks of SD per RECIST criteria;
- Cohort 2: PR with no further reduction in tumor size or response for ≥8 weeks (ie, PR and not improving further)
- Cohort 3: PD with no prior response to anti-PD-(L)1 therapy after ≥8 weeks on anti-PD-(L)1, or
- Cohort 4: Current PD after prior achievement of best response of SD or PR and after ≥8 weeks on anti-PD-(L)1 therapy

Patients will be administered the combination of ALKS 4230 and pembrolizumab. For simplification, the 4 cohorts of patients will be combined into 2 arms:

- Group 1 will consist of all patients with current SD or PR (Cohorts 1 and 2) who are not progressing or further demonstrating reductions in tumor size.
- Group 2 will consist of patients with PD (Cohorts 3 and 4).

Baseline tumor biopsy will be required at the time of study entry after screening procedures have been completed and prior to first administration of combination regimen to assess each patient's tumor characteristics in an effort to identify patients with tumors that may have limited pembrolizumab efficacy or potential response to anti-PD-1/ALKS 4230 combination. Tumors will be assessed for quantity and character of tumor-infiltrating T cells and other leukocytes, and for quantitative assessment of PD-L1 expression, gene signatures that correlate with response or lack of response

Patients will also have a post-treatment (second) biopsy at C1D12, or at any time from C1D8 through C1D19, to assess whether the addition of ALKS 4230 to the treatment regimen alters the TME and what changes on therapy (immunopharmacodynamics) predispose to responses to the combination.

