#### 8.3.10. Tumor Imaging and Assessment of Disease

For the purposes of this study, baseline scans must be done within 28 days before beginning treatment. In addition to a baseline scan, the first on-study imaging time point will be performed

at 6 weeks ( $\pm$  7 days) after first dose, then within 7 days prior to every second cycle thereafter, or more frequently if clinically indicated while the patient is on study.

Patients whose response converts from PD or SD to PR or from PR to CR will have a confirmatory scan for tumor assessments 6 weeks after the response-defining scan. If the patient continues on study after confirmatory scan, then the patient would receive scan per regular schedule. Thereafter, timing of tumor assessments will depend on whether or not the patient continues with study drug (see Table 5 for additional information).

Accumulating evidence indicates that a minority of patients treated with immunotherapy may derive clinical benefit despite initial evidence of PD. Allowance to continue treatment despite initial radiologic progression takes into account the observation that some patients can have a transient tumor flare in the first few months after the start of immunotherapy but with subsequent disease response. Patients will be permitted to continue on treatment beyond initial RECIST v1.1-defined PD as long as they meet the following criteria:

- Investigator-assessed clinical benefit and no rapid disease progression.
- Patient continues to meet relevant eligibility criteria, as determined by the ION and Alkermes Medical Monitors (or designee) in discussion with the Investigator.
- Stable performance status.
- Patient is tolerating study treatment.
- Treatment beyond progression will not delay an imminent intervention to prevent serious complications of disease progression (eg, CNS metastases).

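### In patients with more than one site of disease, a target lesion wholly excised for a study biopsy can meet the PR threshold without any drug effect, and neither document prevents or handles this

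*Protocol*

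**What the plan says.** **Technique.** Inclusion criterion 9 (Protocol 7.1) reads "Biopsy should be excisional, incisional, or core needle and large enough to show tissue architecture". Protocol 8.3.12.1 describes the pretreatment tissue in the same terms: "fresh biopsy via excisional, incisional, or core needle and large enough to show tissue architecture".

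**Obligation.** Section 8.3.12.1 makes both biopsies mandatory, with exceptions. Archived tissue may replace the pretreatment biopsy with the Sponsor's agreement, and the second biopsy may be skipped for safety after discussion with the Sponsor.

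**Timing.** Section 8.1 says "Baseline tumor biopsy will be required at the time of study entry after screening procedures have been completed". Section 8.3.12.1 agrees: "The pretreatment biopsy will be collected after all screening assessments have been performed". Section 8.3.12.1 also says "The pretreatment specimen may be obtained up to 6 weeks (42 days) prior to initiation of treatment on Day 1", while Section 8.3.10 says "baseline scans must be done within 28 days before beginning treatment". The second biopsy is taken from C1D8 to C1D19, at the earlier biopsy site or one like it. The first on-study scan is 6 weeks (±7 days) after the first dose.

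**Target lesions.** Section 8.3.10.2 takes all measurable lesions, up to 2 per organ and 5 in total. It ranks them by size, organ representation and how reproducibly they can be measured. Biopsy is not mentioned.

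**Existing safeguard.** Inclusion criterion 6 begins "Patients with only 1 site of disease must be able to provide adequate tissue samples" and goes on to require that the biopsy leave RECIST tumour size unaffected. It covers only those patients.

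**Endpoint.** PR is a fall of at least 30% in the target sum from baseline (Protocol 8.3.10.4). SD or PD at screening that becomes PR or CR counts as objective improvement (Protocol 11.1, SAP 3.11.2).

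**The concern.** The primary endpoint compares the target sum on study with a baseline measured before treatment. If a target is cut out between those two measurements, it contributes its full diameter to the baseline and nothing to the follow-up. The difference is surgical, but the response criteria as written would read it as tumour shrinkage.

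The overlap between biopsy sites and targets is plausible. Criterion 9 asks for readily accessible tumour, and Protocol 8.3.10.3 lets superficial nodules and palpable nodes of at least 10 mm count as measurable.

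What is at stake is the objective improvement rate in Cohorts 1, 3 and 4, where reaching PR is enough, and the summary of percentage change in target lesions. In a single-arm study no control group carries the same artefact, so nothing offsets it.

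**Working it through.** The plan states no figure on this point, and the planned group sizes are not visible in the public documents.

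**Step 1. Does a biopsy fall between baseline and first response scan?**
- Second biopsy: the latest day is C1D19, which is 18 days after the first dose. The earliest scheduled scan is 42 − 7 = 35 days after the first dose. The biopsy therefore always comes after baseline and at least 17 days before that scan. Tables 5 and 7 give 9 weeks for on-study imaging; that too is after the biopsy.
- Pretreatment biopsy: the general rule puts it after the screening assessments, which include the baseline scan. The specimen may, however, date from up to Day −42, while the scan must be within 28 days of treatment. Some pretreatment biopsies can therefore precede the scan and leave the sum untouched.

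**Step 2. Does any rule catch an excised target?** Protocol 8.3.10.2 (selection), 8.3.10.4 and 8.3.10.5 (response), SAP 3.11.2 (endpoint) and SAP 6.2 (efficacy data handling) contain none. Criterion 6 does, but only for a single site of disease.

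**Step 3. Effect on the target sum.** Assume *k* equal targets, *m* of them excised and the rest unchanged.
- Fall in the sum = *m*/*k*.
- Further shrinkage of the rest needed for PR when one is excised = 1 − 0.7/(1 − 1/*k*).

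| *k* | Fall, *m* = 1 | PR from excision alone? | Further shrinkage of the rest needed | Fall, *m* = 2 |
|---|---|---|---|---|
| 2 | 50.0% | yes | none | not applicable |
| 3 | 33.3% | yes | none | 66.7% |
| 4 | 25.0% | no | 1 − 0.7/0.75 = 6.7% | 50.0% |
| 5 | 20.0% | no | 1 − 0.7/0.80 = 12.5% | 40.0% |

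For unequal lesions, the excised one must carry at least 30% of the baseline sum. Removing the 20 mm lesion from 30 + 20 mm gives 20/50 = 40%, a PR. Removing it from 40 + 20 + 15 mm gives 20/75 = 26.7%, not a PR.

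**Step 4. Incision.** To lower the sum by 30%, incision would have to remove a fraction 0.3*k* of one lesion's diameter: 60% at *k* = 2 and 90% at *k* = 3. At *k* = 4 the fraction is 1.2, which is impossible.

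**Step 5. Confirmation.** The confirmatory scan 6 weeks later still finds the lesion absent, so it does not by itself undo the PR.

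**Step 6. Effect on the rate.** Each such patient adds 1/*n*. The table assumes *n* and no true responders, with the SAP's two-sided 95% Clopper-Pearson interval.

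| Assumed *n* | 0 responders | 1 surgical responder |
|---|---|---|
| 10 | 0% (0 to 30.8) | 10.0% (0.3 to 44.5) |
| 20 | 0% (0 to 16.8) | 5.0% (0.1 to 24.9) |
| 40 | 0% (0 to 8.8) | 2.5% (0.1 to 13.2) |

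If a proportion *f* of patients were affected, the chance of at least one among 20 is 1 − (1 − *f*)^20. That is 33% at *f* = 2%, 64% at 5% and 88% at 10%. These values of *f* are assumptions; the documents give none.

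**The case against.** **Some biopsies cannot matter.** The pretreatment biopsy can precede the baseline scan, and both biopsies have exceptions. A reader might infer that every patient has two cuts after baseline; the documents do not support that. The fixed exposure is the second biopsy, where it is done.

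**Existing text discourages the problem.** Patients need accessible tumour for biopsy before and after treatment, and the second biopsy goes to the earlier site or one like it. Complete removal at the first biopsy is therefore unattractive, though sampling a similar site remains possible. A site might also use the reproducible-measurement rule to pass over a lesion it plans to remove, but nothing requires this. The Laboratory Manual and site procedures, which are not public, may say more.

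**A spurious PR may not last.** This stands in part. PD is judged from the smallest sum on study, and excision lowers that nadir. With two equal targets and one excised, the other could grow by up to 40% (0.7 × 2 − 1) and the sum would still be in the PR range at the first scan. Later growth of at least 20% and 5 mm from the nadir would be PD, as would new lesions or unequivocal non-target progression. Where the remaining disease is merely stable, the PR is confirmed.

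**Incision and core needle.** A reader might infer that any permitted biopsy can create a response. Step 4 shows that incision would have to remove most of a lesion's diameter, and core sampling removes far less. Neither is likely to produce a PR alone.

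**Cohort 2.** By definition it needs CR, so a surgical PR does not count there. The Group 1 formula in SAP 3.11.2 counts CR or PR without that distinction, but this point does not rely on that reading.

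**Conclusion.** The gap is real for patients with more than one site of disease and is confined to wholly excised targets. Followed as written, the plan can count removal of a target carrying at least 30% of the baseline sum as a PR. With four or five equal targets, excision reduces the shrinkage needed elsewhere to 6.7% or 12.5%. The confirmatory scan does not reliably correct this.

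This could inflate the objective improvement rate in Cohorts 1, 3 and 4 and distort the percentage change in target lesions. A reader might infer that the rate will be inflated, or by how much. The documents support neither: they give no excision frequency, no lesion counts and no visible group sizes. The 5 points per patient rests on an assumed 20 per group, and the percentages by lesion number rest on equal-sized targets.

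The remedy is inexpensive and worth making because the primary endpoint is affected.

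**What to change.** 1. **Protocol 8.3.10.2 and criterion 6.** State that a lesion planned for study biopsy is not chosen as a target when another measurable lesion is available. Extend criterion 6's requirement, that biopsy not affect RECIST tumour size, to any target lesion that must be biopsied in any patient.
2. **SAP 3.11.2.** State that a target wholly excised, or reduced in measured size by the procedure, after the baseline scan is removed from both the baseline and follow-up sums. If no target remains, response is not evaluable and the patient stays in the denominator as a non-responder. State also that the rule does not apply to a biopsy that leaves RECIST size unaffected. Otherwise single-site patients admitted under criterion 6 could lose a genuine response, which would bias the rate downward.
3. **eCRF.** Record which lesion was biopsied and by which technique. Rule 2 cannot be applied without this.

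**Cost.** No extra scans are needed. A smaller lesion will sometimes become the target, the wording in 8.3.10.2 that takes all measurable lesions needs this stated exception, and one eCRF field is added. If targets have already been selected, items 2 and 3 still protect the analysis, provided the biopsy details can be recovered.
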